9. ETHICAL CONDUCT OF THE STUDY

The study will be carried out in accordance with the protocol and with principles enunciated in the current version of the Declaration of Helsinki; the guidelines of Good Clinical Practice (GCP) for medical devices, as set forth by ISO 14155:2011 and ISO 14971:2010; applicable sections of US FDA 21 Code of Federal Regulations (CFR); and any other applicable state or national legal requirements in the United States.

The study will be conducted and reported in accordance with applicable policies of the requirements of the Ethics Committee (EC) and governing regulatory authorities.

If national or regional EC requirements are less strict than the requirements of GCP, such as ISO 14155:2011 for medical devices, the Sponsor shall apply the requirements of this International Standard to the greatest extent possible, irrespective of any lesser requirements, and shall record such efforts.

Ethics Committee

The responsible Principal Investigator at each site will ensure that approval from an appropriately constituted EC is attained for the clinical study prior to enrolling subjects, and Principal Investigator will ensure that documentation of approval is maintained for the duration of the study.

The Principal Investigator will ensure that the Sponsor is notified of any withdrawal of EC approval within 5 working days of such occurrence. If approval is terminated or suspended, the Principal Investigator will promptly notify the Sponsor and provide written explanation.

Regulatory Agencies and Competent Authority(ies)

This study will be conducted in accordance with US FDA requirements. Registration with the agency prior to the start of the study is not required for this image evaluation study, in accordance with applicable laws and regulations. Any additional requirements imposed by the EC or regulatory authority shall be followed.

Management of Protocol Modifications and Amendments

Substantial amendments will only be implemented after approval of the EC.

A deviation is any instance(s) of failure to follow, intentionally or unintentionally, the requirements of the protocol. Under emergency circumstances, deviations from the protocol to protect the rights, safety, and wellbeing of human subjects may proceed without prior approval of the Sponsor and the EC/competent authority (CA). Such deviations shall be documented and reported to the Sponsor and the EC as soon as possible. Deviations will be reported as:

- **Critical Deviations:** Deviations that significantly affect the safety, efficacy, integrity, or conduct of the study. These deviations must be reported to the Sponsor no later than 5 working days from awareness of occurrence and reported to the EC per the deviation reporting policy.
- **Non-Critical Deviations:** Protocol deviations that do not significantly affect the safety, efficacy, integrity, or conduct of the trial. These deviations must be documented on the CRF Protocol Deviation page and will be reviewed by the study monitor.

Non-substantial modifications may be made during the normal course of device optimization, maintenance, and feasibility testing. Non-substantial modifications will be communicated to the CA as soon as possible, if applicable, and to the EC per their policy.

■ Participant Information and Informed Consent

The investigators will explain to each participant the nature of the study, its purpose, the procedures involved, the expected duration of exposure to the investigational device (if applicable), the potential risks and benefits, and any potential discomforts. Each participant will be informed that participation in the study is voluntary, that he/she may withdraw from the study at any time, and that withdrawal of consent will not affect his/her subsequent medical assistance and treatment. The participant must be informed that his/her medical records may be examined by authorized individuals other than their treating physician.

All participants for the study will be provided an ICF, describing the study and providing sufficient information to allow the participant to make an informed decision about his/her participation in the study. Informed consent documents will be subject to approval by the EC prior to enrolling subjects in the study.

The participant should read and consider the statement before signing and dating the ICF, and shall be given a copy of the signed document. The ICF must also be signed and dated by the investigator (or his/her designee), and it shall be retained as part of the study records.

■ Early Termination of the Study

The Sponsor may terminate the study prematurely according to certain circumstances. Examples of such circumstances include ethical concerns, insufficient participant recruitment, participant safety concerns, alterations in accepted clinical practice that make the continuation of a clinical trial unwise, early evidence of benefit or harm of the research product, or for any other reason.

10. STATISTICAL METHODS

■ Statistical Hypothesis

No statistical hypothesis is being prospectively tested in this study. As necessary for regulatory submission, additional analyses will be detailed prior to the star to independent reads in the Statistical Analysis Plan (SAP) prepared by the Sponsor's biostatistician.

■ Sample Size Determination

The sample size is based on the Sponsor's engineering determinations of the required number of sample images, and is not prospectively powered to produce statistically powered results. The protocol aims to acquire 30 images using Q Static (Q. MRAC) and 30 images using ZTE. Datasets may include one or both image type, based on clinical availability, to meet these targets. Assuming that 10% of cases will include both types of data and 25% attrition rate due to various causes, this study requires a population (N) such as that:

$$1.1N - (1.10 \times N)(0.25) = 30 \text{ ZTE} + 30 \text{ Q static}$$

Study Title: Clinical Evaluation Of MP26 Features in Adults

Study No: 114.03-2016-GES-0001

To satisfy this requirement, a minimum population size of $N = 72$ is required. This is approximated to $N = 75$, as this number is considered by the Sponsor to be sufficient to account for unforeseen contributions to dropout or evaluable image rates.

■ Statistical Analysis

■ General Statistical Methods

The study data will be presented in tables, listings, and figures. Data will be summarized using descriptive statistics. The descriptive statistics for variables will include mean, standard deviation, median, Q1 and Q3, minimum, maximum, and count. Categorical variables will be described with counts, percentages. If necessary for regulatory submission, additional statistical methods may be employed as detailed in the Statistical Analysis Plan (SAP) prepared by the Sponsor's responsible biostatistician and stored in the study's clinical history file (CHF).

■ Analysis Set(s)

The study analysis sets include the Safety Population and Per-protocol population.

The safety population includes all subjects enrolled and scanned, the per-protocol population include all subjects enrolled, scanned, processed with ZTE and/or Q-static and without critical protocol deviation.

■ Analysis of Primary Endpoint(s)

General descriptive statistical methods will be used to summarize the study diagnostic image quality results by reader and overall.

■ Analysis of Secondary Endpoint(s)

General descriptive statistical methods will be used to summarize each secondary endpoint.

■ Safety Analysis

Tables and listings of safety events, deviations, and device issues will be prepared, including counts and percentages as appropriate.

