4. STUDY DESIGN

Study Population

Subjects will be enrolled that have a clinical indication for PET/CT or PET/MR with radiotracer injection prescribed for their medical care outside of the study. Sites should make reasonable attempts to ensure diversity of clinical state (including injury severity or extent of disease progression) within the enrolled population in order to achieve a sample maximally representative of the intended use population.

Number of Subjects

The study aims to acquire up to 75 clinical PET/MR image sets (up to 38 subjects will be enrolled to have a ZTE MRAC exam and the remaining 37 subjects will be enrolled to have a Q Static (Q. MRAC) exam. In the event that a subject scan does not produce images, as in the case of withdrawal or technical issues preventing scanning, additional subjects may be enrolled until the target number is achieved (not to exceed a maximum of 75 subjects during the course of the study) as described in [Section 10.2 - Sample Size Determination](#). The minimum number of necessary subjects will be enrolled to achieve the target number of datasets.

Enrollment Quota

Subjects will be enrolled based on a quota block method based on scan type (relative to the patient clinical indication for PET/CT or PET/MR). Each subject may have only one type of scan towards these quota blocks (ZTE or Q.Static MRAC), not both (Table 1).

Table 1. Target quota blocks for subject enrollment/target datasets

Scan Type	Target number of subject datasets ($N_{\text{Target}} = 30$)
ZTE MRAC	At least 30 subject scans ($N_{\text{neuro}} = 30$ to 38)
Q Static (Q. MRAC)	At least 30 subject scans ($N_{\text{body}} = 30$ to 37)

Protection of Vulnerable Subjects

Vulnerable subjects are individuals whose willingness to volunteer in a clinical investigation could be unduly influenced by the expectation, whether justified or not, of benefits associated with participation or of retaliatory response from senior members of a hierarchy in case of refusal to participate. The Sponsor shall avoid improper influence on, or inducement of, the subject, monitor, any investigator(s), or other parties participating in, or contributing to, the clinical investigation.

All investigators shall avoid improper influence on, or inducement of, the subject, Sponsor, monitor, other investigator(s), or other parties participating in, or contributing to, the clinical investigation.

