The device operator will acquire scan data using default PET/MR scan protocols, default MR-only scan protocols, and other scanning protocols optimized by the operator as appropriate for the subject's clinical state. The scan protocols and associated pulse sequences used shall be chosen by the investigator. For PET/MR simultaneous scanning, the first scan will be a whole body localizer. The user will then define n beds ($n \leq 14$). The user will have the option to insert as many MR scans at each bed position, although a MR attenuation correction scan will always be acquired first at each bed position (approximately a 30 second scan). The PET will continue to acquire data until the time set by the

operator has elapsed. The system will then automatically move to the next bed position. The user will be able to view the PET images overlaid on the MR images from each bed after it has been reconstructed.

During each scan, the operator should complete ZTE MRAC or Q Static (Q. MRAC) protocol appropriate for the subject's indication, and record the sequence used in the exam. For Q Static (Q. MRAC) scans, the site should conduct 5 non-gated MRAC acquisitions and 5 gated acquisitions for each subject around the lung/abdominal region including the diaphragm. For all scans, the device operator should attempt to complete both PET and MRI scans on the PET/MR system and to collect an image set that includes both PET and MRI images. At the end of each scan session, the device operator will record information about the device used, the time of the scan session and his/her observations in the Case Report Forms (CRFs). If the device operator is unable to collect both PET and MRI images, he or she should record the reason on the Case Report Form (CRF). The device operator will save the images and raw data.

Table 2. Characteristics recorded to the CRF during PET/MR scan sessions

Coil(s) Used	Gating device(s) used	Medical tubes wires/cables

 3.0T PET/MR CMA 3.0T HNU 3.0T UAA 3.0T LAA GEM Flex Coil 16-S, M, L Array 3.0T Split head coil PETMR 8Ch HiRes Brain Array 3.0T HD Flat GEM Table Breast Array Other, specify 	
 Respiratory bellows ECG leads Peripheral gating photopulse sensor 	
 None IV Catheterization Breathing tube Oxygen ECG Monitor Other, specify

Emergency Procedures

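### Section 10.2 still credits 10% of subjects with both scan types, which the design excludes; at 25% attrition, 60 expected datasets need 80 subjects, not 72, and the cap of 75 gives about 56.

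*Combined protocol and SAP*

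**What the plan says.** Section 10.2 (Sample Size Determination) sets a target of 30 ZTE and 30 Q.Static images. It allows one subject to count toward both: "Datasets may include one or both image type, based on clinical availability, to meet these targets". It then makes two assumptions, "Assuming that 10% of cases will include both types of data and 25% attrition rate due to various causes", and solves 1.1N − (1.10 × N)(0.25) = 30 + 30. From this it concludes that "a minimum population size of $N = 72$ is required". It raises this to 75 on the ground that "this number is considered by the Sponsor to be sufficient to account for unforeseen contributions to dropout or evaluable image rates".

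The design sections say otherwise. Section 4.2.1 (Enrollment Quota): "Each subject may have only one type of scan towards these quota blocks (ZTE or Q.Static MRAC), not both (Table 1"). Section 5.2.2 (scanning procedure): "the operator should complete ZTE MRAC or Q Static (Q. MRAC) protocol". Section 4.2 (Number of Subjects) splits enrolment into up to 38 ZTE and 37 Q.Static subjects and limits replacement: "additional subjects may be enrolled until the target number is achieved (not to exceed a maximum of 75 subjects". The per-protocol definition in Section 10 keeps similar both-types wording: "processed with ZTE and/or Q-static and without critical protocol deviation".

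**The concern.** The sample size section and the design sections are all operative text in version 4.0, and they describe different studies. In one, a tenth of subjects supply two datasets; in the other, none can. The version control entry for version 3.0 shows that one exam per subject was a deliberate choice. Appendix C lists conforming edits to Sections 4.2 and 5.2.2 but none to Section 10, which fits a paragraph that was missed.

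This paragraph is the only derivation of N = 75, and the number of images is the stated basis for the sample size. If the credit is invalid, the study cannot be expected to reach its own target at its own attrition rate, and the margin claimed for 75 does not exist.

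**Working it through.** **Inputs.** Target 30 + 30 = 60 datasets, dual-type credit 10% and attrition 25% (Section 10.2). Cap of 75 subjects including replacements, split 38/37 (Section 4.2). One scan type per subject (Sections 4.2.1 and 5.2.2).

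**1. The plan's own figure.** The equation reduces to N = 60 / (1.1 × 0.75) = 72.7, so the stated 72 is reproduced apart from rounding. Strictly, 72 gives 1.1 × 0.75 × 72 = 59.4 and 73 gives 60.2, so the smallest whole N is 73. This slip is covered by 75 and has no effect. The fault lies in the 1.1, not in the algebra.

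**2. One dataset per subject.** Expected datasets = N × (1 − attrition), so N = 60 / 0.75 = 80, or 30 / 0.75 = 40 per scan type.

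**3. Expected yield.**

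| | Subjects | Expected at 25% attrition | Target | Gap |
|---|---|---|---|---|
| Stated minimum | 72 | 54.0 | 60 | 6.0 |
| Cap, total | 75 | 56.25 | 60 | 3.75 |
| Cap, ZTE | 38 | 28.5 | 30 | 1.5 |
| Cap, Q.Static | 37 | 27.75 | 30 | 2.25 |

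**4. What the credit is worth.** At N = 75 it adds 75 × 0.10 × 0.75 = 5.6 datasets. The protocol states no expected yield, but its formula at N = 75 gives 1.1 × 0.75 × 75 = 61.9. The credit thus separates 1.9 above target from 3.75 below it.

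**5. Break-even attrition at the cap.** ZTE: 1 − 30/38 = 8/38 = 21.05%. Q.Static: 1 − 30/37 = 7/37 = 18.9%. Both are below the planned 25%.

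**6. Illustration only.** If losses were independent at exactly 25%, the binomial chance of at least 30 datasets would be 0.36 for ZTE (n = 38), 0.26 for Q.Static (n = 37) and 0.09 for both. Losses at a single site could cluster, so these figures only indicate scale.

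**7. Table 1.** Its cells count scans, not evaluable datasets, and the documents do not divide the 25% into losses before and after scanning. If, for example, 15% were lost before scanning, there would be 38 × 0.85 = 32.3 ZTE scans and 37 × 0.85 = 31.5 Q.Static scans. The scan quotas are therefore not shown to be missed.

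**The case against.** The strongest reply is that little depends on this number. The protocol tests no hypothesis, disclaims power, rests the image count on engineering judgement and summarises every endpoint descriptively. The 30 + 30 is an aim, Section 4.2 already makes it subject to the cap, and results may be combined with concurrent studies for submission. All of that stands, and it limits the weight of the point: no planned summary becomes invalid with about 28 datasets per feature. It does not rescue the derivation. The documents do not say that other studies count toward these 60 datasets, and replacements cannot close the gap because they fall within the 75.

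It is also fair to call this an outdated input rather than an arithmetic error, since the stated 72 follows from the equation as printed. The input is nonetheless one that the design excludes, so the stated minimum is wrong for this study.

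Finally, the and/or phrase in the per-protocol definition classifies nobody differently when each subject has one exam. Correcting it is only tidying.

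**Conclusion.** The concern holds: Section 10.2 is wrong as written. With one scan type per subject and the protocol's 25% attrition, 60 expected datasets require 80 subjects, not 72. The cap of 75 gives 56.25, short by 1.5 ZTE and 2.25 Q.Static datasets, so the statement that 75 is sufficient does not follow.

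This rests on reading the 25% as the overall loss from enrolment to evaluable dataset, applied equally to both scan types, as the section's equation applies it. It concerns expected counts: at lower attrition the targets could still be met. The point should be fixed, but its consequence is modest.

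**What to change.** In Section 10.2:

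1. Delete the 10% dual-type assumption and the sentence allowing a dataset to contain both image types.
2. Replace the equation with: expected datasets = N × (1 − attrition).
3. Replace the stated minimum with: *At 25% attrition, 60 expected datasets would need N = 80 (40 per scan type).*
4. Keep the cap at 75 and add one of two statements:
   - (A) *With up to 75 subjects (38 ZTE, 37 Q.Static) and 25% attrition, about 56 evaluable datasets, about 28 per feature, are expected; 30 + 30 remains an aim subject to the cap.*
   - (B) *30 + 30 datasets are expected only if attrition is at most 21.0% (ZTE) and 18.9% (Q.Static)*, with the reason for planning on less than 25%. The ZTE figure is rounded down from 21.05% so that the condition is met.
5. Delete or qualify the statement that 75 is sufficient for unforeseen dropout.

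In the per-protocol definition, change and/or to or. Leave the Table 1 quotas as they are. It would help to say whether they mean completed scans or evaluable datasets, since the header and the cells differ.

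The cost is one rewritten paragraph and one changed word, with no extra patients and the cap and 38/37 split unchanged. The price is a slightly less favourable stated yield under (A), or the need to defend a lower attrition rate under (B). Raising the cap to 80 would restore 60 datasets in expectation, but it adds five subjects and is not needed for a descriptive study.

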3. STUDY OBJECTIVES AND ENDPOINTS

■ Purpose of the Study

The purpose of the study is to collect representative clinical images with demonstrated diagnostic image quality using ZTE MRAC and Q Static (Q. MRAC) software features. The images and summary data from this study are intended for use in regulatory submission(s).

■ Primary Objective:

To demonstrate diagnostic image quality of image sets with ZTE MRAC and Q Static (Q. MRAC) for SIGNA PET/MR in representative clinical cases of the general imaging population.

■ Secondary Objective(s):

To verify diagnostic acceptability, ease of use, and functionality of ZTE MRAC and Q Static (Q. MRAC) for SIGNA PET/MR at clinical sites.

■ Safety Objective(s):

To collect information about safety events and device issues.

■ Study Endpoints

■ Primary Endpoints:

Independent radiologist/nuclear medicine physician determination of diagnostic image quality considering all evaluable images from each subject (scored on a 5-pt Likert scale)

■ Secondary Endpoints:

Site level determination of diagnostic acceptability (Y/N) based on consensus between radiologist(s) and nuclear medicine physician(s) at the site

Ease of use per procedure rated on a 5-pt Likert scale score

Functionality rated for each feature per procedure on a binary (Y/N) performance scale

■ Safety Endpoints

Type and number of safety events (AEs and SAEs) and device issues (malfunctions, user errors, and labeling issues) will be summarized.

■ Summary of Study Design

This is a pre-market, open label, prospective, non-randomized clinical research study at one site. The study is designed to allow for sample PET/MR image collection and to demonstrate diagnostic image quality of resultant sample image sets from each participating subject. The results of this study will be analyzed according to a prospective Blinded Image Evaluation (BIE) plan and Statistical Analysis Plan (SAP) prepared by the Sponsor prior to the start of image reads. This study is run concurrently with other studies of the device conducted by the Sponsor and it is prospectively expected that the cumulative results of these studies may be used to support regulatory submissions.

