In the event of a medical emergency, the scan will be stopped immediately and facility's emergency response plan will be followed. The subject will be provided with emergency care as needed.

The subject's care shall take precedence over any imaging associated with the study. In the event the subject experiences discomfort or wishes to stop the exam for any reason, the exam will be immediately stopped and appropriate follow up response will occur. The event will be recorded in compliance with US FDA and GE Healthcare safety reporting requirements.

Incidental Findings

The additional PET/MR procedures performed in this study are for research only and are not intended for diagnostic use. Should the device operator observe what they interpret to be a potential abnormality, the investigator will evaluate the findings and alert the patient if necessary. The investigator may recommend diagnostic exams to be performed independent of the study. No medical or diagnostic care of any kind will be rendered based on study image sets using the research PET/MR.

Activities after PET/MR Scanning

Upon completion of the exam, the device operator or those assisting him/her will assist the subject from the device and out of the scan area. Any reported safety or device issues will be recorded to the CRF up until the time the subject leaves the PET/MR suite.

After the exam is complete and the subject has left the PET/MR suite, the device operator will complete the CRF and store the image sets for the scan, which will be labeled with the subject's unique ID number. All images collected from clinical sites will be sent to the Sponsor or its delegate for investigational post-processing with the investigational technology prior to image reads.

Follow-up Visits

All patient procedures will be conducted during a single visit. No follow-up visits are required.

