The reader should record the rationale for any "no" answer indicating that the image is not acceptable quality for diagnostic use. And/or provide comments in image annotation or point to the problem area in the images. Scores should be based on all views included in the image set, considering all available views, with the exception of the LAVA sequence used for MR-attenuation correction (which should not be considered in the evaluation for image quality).

Ease of use

Each of the following **ease of use** parameters will be rated by the device operator on a 5-point scale (1 = challenging, 2 = somewhat challenging, 3 = neutral neither challenging nor easy, 4 = somewhat easy, 5 = easy), where scores of ≥ 3 are acceptable, as follows:

- Prescribing and Scanning
 - Prescribing PET scan
 - Prescribing MR scans simultaneous with PET
 - Starting and monitoring scanning
 - Reviewing PET and MR image sets
- General Workflow
 - Overall process of doing this exam
 - Performing exam within acceptable duration to meet normal site workflow requirements

Functionality

Each of the following parameters for **functionality** will be rated by the device operator on a binary (Y/N) scale, as follows:

- Did the system function to view the PET, MR, and/or fused image sets?
- Did the system function to position subject and coils in scanner?
- Did the system function to prescribe and scan this exam? If no, indicate which (PET, MR, and/or fused did not function properly).

If no is indicated for any functionality, the investigator should indicate the reason in a provided area for comments on the Case Report Form (CRF).

Safety Assessments

The description, severity, and device relatedness of any AE or SAE during the study will be recorded. Subjects will, if necessary, be provided with emergency care. In the event of any device issues, the event will be recorded. Safety reporting will be conducted as described in this protocol.

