10.3 Interim Analysis

No interim analyses are prospectively planned as part of this study.

■ Handling of Missing Data

Analysis will be based on collected data, and no imputation will be done for missing data.

■ Deviation(s) from the Original Statistical Plan

Any changes or deviations from the original statistical plan specified in this protocol will be described and justified in the SAP and/or study final report as required by ISO 14155:2011.

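### If either defined analysis set is applied, exams the system could not scan drop out of the functionality and ease-of-use summaries

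*Combined protocol and SAP*

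**What the plan says.** Section 3 makes verification of functionality and ease of use part of the secondary objective and defines the endpoints as "Functionality rated for each feature per procedure on a binary (Y/N) performance scale" and "Ease of use per procedure rated on a 5-pt Likert scale score". In Section 6 the device operator gives the ratings. One functionality item reads "Did the system function to prescribe and scan this exam"; a negative answer must name the part that failed (PET, MR or fused), with a reason.

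Section 10 defines two analysis sets. The safety population is the subjects who were enrolled and scanned. The second is narrower: "the per-protocol population include all subjects enrolled, scanned, processed with ZTE and/or Q-static and without critical protocol deviation". For the secondary endpoints the analysis is "General descriptive statistical methods will be used to summarize each secondary endpoint", with no set named. On missing data: "Analysis will be based on collected data, and no imputation will be done for missing data".

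Section 4 foresees exams that yield no images. In the case of withdrawal or "technical issues preventing scanning, additional subjects may be enrolled until the target number is achieved", up to a maximum of 75 subjects.

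On the timing of the form, Section 5 says "After the exam is complete and the subject has left the PET/MR suite, the device operator will complete the CRF". The scanning procedure in the same section places recording at the end of the scan session, and Section 11 asks for CRFs to be filled in as information becomes available.

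**The concern.** The two operator-rated endpoints describe the attempt to run the exam. Unlike the independent read and the site Y/N read, which Section 6 limits to evaluable image sets, they need no processed images, and Section 6 places no such limit on them.

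The only sets on offer nevertheless select on a completed step of the exam. For the prescribe-and-scan item, membership of either set depends on the outcome being measured: an exam that could not be scanned is the clearest negative answer, and it belongs to neither set. A reported rate of 100% could then describe a system that never failed or one that failed several times before the dataset target was met. Section 2 says the results are intended for a 510(k) submission, so a reader outside the study may see the percentage without knowing what was left out of it.

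**Working it through.** **The plan's own figures.** The protocol states no functionality rate, so there is none to reproduce. The nearest figure is the sample size. Solving the Section 10 equation gives N = 60 / (1.10 × 0.75) = 72.7, against 72 stated and 75 adopted, so it reproduces to within rounding. The 25% attrition in that equation is attributed to various causes with no share given for system failure. The number of unscannable exams therefore cannot be derived from the plan and has to be assumed.

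**Where each kind of exam lands.**

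| Exam | Safety population | Per-protocol set |
|---|---|---|
| Completed and processed, no critical deviation | in | in |
| Started, then failed in PET, MR or fusion, with something to process | in, if it counts as scanned; can be an N | in, unless there is a critical deviation |
| Started, then failed, with nothing to process | in, if it counts as scanned; can be an N | out |
| Could not be scanned at all | out | out |
| Completed, but post-processing failed or a critical deviation occurred | in, possibly with a Y | out |

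Neither *scanned* nor *procedure* is defined, so the second and third rows depend on interpretation. The fourth row does not.

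**Direction of the effect on the prescribe-and-scan item.** Let y and n be the Y and N answers among scanned exams, and k the exams the system could not scan, each a true N.

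- Safety population: reported rate y / (y + n); all-attempts rate y / (y + n + k). For k > 0 and y > 0 the first is always the larger.
- Per-protocol set: the last row of the table can also remove Y answers. Removing Y answers lowers y / (y + n) whenever n > 0, while removing N answers raises it. The net direction is not fixed.

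For the other items the direction is not settled even under the safety population. For example, subject and coils may have been positioned without trouble before an exam that then could not be scanned.

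**Illustration.** Inputs: 60 completed, functioning exams (the Section 10 target of 30 ZTE plus 30 Q Static); k assumed; exact (Clopper-Pearson) 95% intervals.

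| k (assumed) | Scanned only | All attempts, 60 / (60 + k) |
|---|---|---|
| 0 | 60/60 = 100% (94.0 to 100) | 60/60 = 100% (94.0 to 100) |
| 3 | 60/60 = 100% (94.0 to 100) | 60/63 = 95.2% (86.7 to 99.0) |
| 5 | 60/60 = 100% (94.0 to 100) | 60/65 = 92.3% (83.0 to 97.5) |

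For one feature with 30 completed exams, three unscannable exams move the rate from 30/30 = 100% (88.4 to 100) to 30/33 = 90.9% (75.7 to 98.1).

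**The case against.** The strongest reply is that the plan never assigns these endpoints to either set. An N written on a CRF is collected data, not a missing value, so the no-imputation rule does not remove it. The detailed SAP was still to be written before the reads and could name a suitable denominator. This stands, and it is why the point is conditional. But nothing in the current text would lead the SAP's author to a denominator of all attempts, because the only sets on offer exclude the exams in question.

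Several stronger readings are tempting, and the documents do not support them:

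- *The functionality rate cannot register failure.* This is true only of exams with no scan at all, and only if a defined set is applied. A scan that starts and then fails can be an N in the safety population, and Section 5 requires a reason on the CRF when PET and MRI are not both collected.
- *Failures are hidden.* Malfunctions are a safety endpoint, and device issues are tabulated and listed. However, no passage links those tables to the functionality rate.
- *Failed exams are automatically replaced.* Section 4 says further subjects may be enrolled; it does not discard the failed subject's data.
- *The form is completed only after a finished exam.* Sections 5 and 11 also give other timings. What is missing is an explicit instruction for an exam that never starts.
- *The bias always favours the device.* That holds for the prescribe-and-scan item under the safety population, not under the per-protocol set.
- *The rate could be overstated by 20 points.* The cap leaves room for 75 − 60 = 15 further subjects, and 60/75 = 80.0%. That figure treats every one of them as a total system failure, while Section 5 lists other reasons for withdrawal, such as missing PET/CT images.

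The study is also descriptive, with no hypothesis and no stated pass mark for functionality, which limits the consequence.

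**Conclusion.** The point holds in conditional form. Both defined sets require a scan, the secondary analysis names no other denominator, and one item asks whether the scan could be done. Applying either set therefore conditions that item on its own outcome and drops unscannable exams from the ease-of-use scores as well. For the prescribe-and-scan item under the safety population the reported rate can only be too high. Under the per-protocol set, partial failures that leave nothing to process are also lost, with no fixed net direction.

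The size depends on k, which the documents do not give. With 60 completed exams, three to five unscannable ones would turn a reported 100% into 95.2% to 92.3%. This assumes that every completed exam is rated Y and that each unscannable exam is a system failure. For a descriptive secondary endpoint the point should be corrected, but it does not touch the primary endpoint.

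**What to change.** Add to the secondary analysis, in substance:

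> Functionality and ease of use are summarised separately for ZTE and Q Static over all subjects in whom a research PET/MR exam was attempted, including exams not started, aborted, replaced or unprocessed because of a system failure. The operator form is completed for every attempt. A functionality item not achieved because the system failed is recorded as N; this is a recorded outcome and is consistent with the no-imputation rule. Ease-of-use items not reached are reported as a count beside the scores. Attempts ended for non-device reasons, such as subject withdrawal, are reported separately by reason and are not counted as N.

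Define *scanned*, *procedure* and the start of an attempt. Entry to the PET/MR suite is a natural choice for the last, since device issues are already recorded from that point. Report the number of subjects replaced and why, by feature. Keep the site Y/N image read on evaluable image sets.

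The cost is SAP wording and a CRF instruction, with no added subjects, scans or readers. The downside is that the functionality rate may come out lower and that the reason for every incomplete attempt has to be coded.
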